12.3 Treatment assignment

Subjects who have been found to comply with all the inclusion criteria and not to violate any of the exclusion criteria will be randomized at baseline (visit 2) to receive treatment with either brodalumab or placebo. Treatment assignment will be according to a computer generated randomization (REDCap, <https://redcap.au.dk>) in a 1:1 ratio. The method of randomization will be based on matched pairs design in which subjects will be matched on sex and age stratification (age decades; 40 – 49, 50 – 59, 60 – 69, 70 – 79, > 80).

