10.1 Overall trial design

This is an investigator-initiated, single-center, randomized, double-blind (subjects, investigators, and nuclear medicine specialists and all staff involved in vascular imaging and analysis is blinded to group assignment) prospective, controlled study. Subjects are randomized and matched on sex and age (\pm 5 years) (stratified randomization).

Subjects with moderate-to-severe psoriasis are enrolled consecutively and randomly assigned to either active treatment with brodalumab or placebo during the treatment period. Subjects are entered into a pre-study washout period, if needed, wherein all active anti-psoriatic topical and systemic therapies are discontinued according to pre-specified time frames.

Psoriasis subjects are examined with FDG-PET/CT at baseline and again at end of study after 16 weeks of brodalumab treatment or placebo, respectively.

Baseline investigations include medical history, physical examination, and laboratory tests.

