10.2 Number of subjects needed

Assuming a screening failure rate of 20%, approximately 62 patients will be screened and 50 patients will be included and randomly assigned to either brodalumab or placebo (1:1; 25 patients in each arm).

The statistical power calculation (section 14.1) includes the risk of drop-out before completion of the second FDG-PET/CT.

Trial ID (EudraCT No.): 2017-003697-14	Date: 23.02.2018	Page Version 2.3
---	------------------	---------------------

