11.2 Inclusion criteria

1. Written informed consent obtained from the subject prior to performing any protocol-related procedures.
2. Age 40 and above.
3. Diagnosis of chronic plaque psoriasis confirmed by a dermatologist
4. PASI \geq 10

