15.1 Sample size

Derived from our investigations of vascular inflammation in psoriasis patients and control subjects, we expect a mean aortic TBR_{max} of 2.4 with a standard deviation of 0.35 in the psoriasis subjects. After successful treatment with biologic agents, we expect the MeanTBR_{max} in the psoriasis subjects to be reduced to 2.1 with SD 0.35. Based on these assumptions and an alpha-level of 0.05 we calculate that 22 psoriasis subjects in each study arm will provide a power of 80% to detect a difference between the groups. By choosing a sample size of 25 psoriasis subjects we allow for a dropout of 3 subjects at follow-up without reducing power significantly.

Trial ID (EudraCT No.): 2017-003697-14	Date: 23.02.2018	Page Version 2.3
---	------------------	---------------------

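### Sections 10.1 and 12.3 state two different age rules for the randomisation, the last age group read literally omits age 80, and the primary model carries neither rule

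*Protocol*

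**What the plan says.** Protocol section 10.1 (Overall trial design) states "Subjects are randomized and matched on sex and age", gives the age tolerance as plus or minus 5 years, and labels the procedure stratified randomisation.

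Protocol section 12.3 (Treatment assignment) states "The method of randomization will be based on matched pairs design in which subjects will be matched on sex and age stratification", and lists the age groups as "40 – 49, 50 – 59, 60 – 69, 70 – 79, > 80". It also gives the 1:1 ratio and names REDCap as the system that generates the allocation.

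Section 11.2 sets the age criterion as "Age 40 and above". Neither 11.2 nor the exclusion criteria in 11.3 set an upper limit. Section 10.2 gives the size: "50 patients will be included and randomly assigned to either brodalumab or placebo (1:1; 25 patients in each arm".

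Section 15.4.1 analyses the primary endpoint with a repeated measurements model and names no randomisation factor in it. Age (continuous) and gender appear only in a supportive analysis, to be done if applicable.

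**The concern.** The protocol fixes its allocation rule twice, and the two statements differ. They also differ in kind. A 5-year tolerance compares two individuals, decades are fixed strata, and matched pairs and stratified randomisation lead to different natural analyses. Someone building the allocation list from 10.1 and someone building it from 12.3 could produce different schemes, and no section says which governs.

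Two things are at stake. The first is conduct: an eligible subject aged 80 would have to be placed by a decision made at the time of randomisation, which a prespecified scheme should make unnecessary. The second is analysis: a standard error that respects the design needs the factors actually used, and here their definition is ambiguous and the primary model leaves them out.

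**Working it through.** **1. Does either rule imply the other?**

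| Ages of two subjects of the same sex | Within 5 years (10.1) | Same age group (12.3) |
|---|---|---|
| 42 and 45 | yes | yes |
| 40 and 49 | no (9 years) | yes |
| 49 and 50 | yes (1 year) | no |

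The rules overlap, but neither contains the other. The 5-year rule is also not transitive: 44 matches 49 and 49 matches 54, but 44 and 54 are 10 years apart. On its own it therefore does not define strata, although 10.1 uses that label.

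**2. How often do the rules disagree?** The protocol gives no age distribution. Purely as an illustration, assume uniform integer ages.

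- Same decade but more than 5 years apart: differences of 6, 7, 8 and 9 give 2 × (4 + 3 + 2 + 1) = 20 of 100 ordered pairs, or 20%.
- Within 5 years, ages 40 to 79: 40 + 2 × (39 + 38 + 37 + 36 + 35) = 410 ordered pairs. Each of the three decade boundaries is crossed by 2 × (1 + 2 + 3 + 4 + 5) = 30 of them, so 90 of 410 (22%) fall in different decades.

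Other age distributions move both fractions widely. Each is 0 if all subjects are the same age. The first is 50% if ages split evenly between 40 and 49, and the second is 50% if they split evenly between 49 and 50 (2 × ½ × ½ in each case). The two fractions describe two alternative schemes, only one of which would be run.

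**3. Do the listed groups cover every eligible age?** Mapping each integer age from 40 to 100 to the list in 12.3 leaves one age without a group: 80. Writing the last group as 80 and above closes the gap.

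**4. Is the sample size affected?** Inputs from section 15.1: means 2.4 and 2.1, SD 0.35, alpha 0.05 (two-sided per 15.4.1), power 80%.

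n per arm = 2 × (1.960 + 0.842)² × (0.35 / 0.30)² = 2 × 7.85 × 1.361 = 21.4, so 22.

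This reproduces the protocol's 22 per arm with an unpaired two-group formula. Neither age rule enters it, and no gain from pairing is claimed.

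**5. What does leaving the factors out do to the standard error?** Let R² be the share of the outcome variance in the primary comparison that sex and age group explain. When allocation is balanced within these groups, the true variance of the treatment difference is about 2σ²(1 − R²)/n. A model without the factors estimates about 2σ²/n. The reported standard error is then too large by a factor of 1/√(1 − R²). The protocol gives no R², so I assume a range:

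| Assumed R² | Inflation of standard error |
|---|---|
| 0 | 1.00 |
| 0.05 | 1/√0.95 = 1.03 |
| 0.10 | 1/√0.90 = 1.05 |
| 0.20 | 1/√0.80 = 1.12 |

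**6. What does including them cost?** With 22 analysed per arm, a two-group comparison has 44 − 2 = 42 residual degrees of freedom. Sex (1) and five age groups (4) reduce this to 37; merging the top two groups gives 38. The two-sided 5% critical value of t moves from 2.018 to 2.026 or 2.024, an increase of about 0.4%.

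**The case against.** Section 10.1 is an overview. Section 12.3 is the operative text, naming the system, ratio and groups, and a list builder would naturally follow it. A ten-year band is its midpoint plus or minus about 5 years, so the tolerance in 10.1 may be loose shorthand for the same bands. The last group is probably a slip for 80 and above: section 8.10 writes the enrolment limit as above 40, where 11.2 admits age 40. Section 8.10 also puts the typical mean age in such trials at about 40 to 50 years, so a subject aged exactly 80 among 50 is unlikely. Covariates in the primary model could be settled in the SAP, which is not shown.

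Most of this stands and limits the size of the point. It does not remove the point, because the protocol nowhere says that the tolerance is shorthand, and two sections that fix one rule differently can be reconciled only in the protocol.

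A reader might infer more than the text supports:

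- *That no allocation table can satisfy both sections.* Five-year bands nested within the decades (40 to 44, 45 to 49, and so on) keep every pair in one decade and at most 4 years apart, which meets both limits.
- *That some five to seven of 25 pairs are affected.* Such a figure multiplies 25 by 20% (5 pairs) and by 27% (6.8 pairs). The 27% is 30 of 110 for a decade with neighbours on both sides, and it ignores the eligibility floor at 40. It merges two alternative schemes under an assumed age distribution, and a pair counted this way merely fails the rule that was not used.
- *That the treatment comparison is biased.* Allocation is random and 1:1 under either rule.

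**Conclusion.** The inconsistency is real and can be read directly from the protocol. Sections 10.1 and 12.3 state different allocation rules, neither implies the other, and the age groups as printed omit one eligible age. The practical size is small. There is no bias, the sample size is unchanged, and the gap at 80 is probably typographical and unlikely to be met among 50 subjects.

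The remaining consequence is for precision. The allocation factors are ambiguous and are absent from the primary model in 15.4.1, so its standard error would not reflect the restricted randomisation. The usual direction is conservative, by roughly 0 to 12% if sex and age group explain 0 to 20% of the variance. That range is an assumption. The case for correction rests on the contradiction itself, which depends on no assumed age distribution.

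**What to change.** - State one rule in both sections: 1:1 randomisation stratified by sex and age group, with the groups of 12.3. Delete the 5-year tolerance from 10.1, and drop the matched-pairs wording from 12.3 so that the design has one name.
- Write the last group as 80 and above, or merge it into 70 and above, so that every eligible age falls in exactly one group.
- Include sex and age group as main effects in the primary repeated measurements model, with sparse groups merged. Do not use sex-by-age cells: 2 × 5 = 10 cells for 50 subjects would leave some nearly empty. If baseline and week 16 are both modelled as responses, give these factors visit-specific coefficients, because an effect that is constant over visits cancels out of the change.

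The cost is wording in 10.1, 12.3 and 15.4.1, one setting in the REDCap allocation table, and four or five degrees of freedom. No sample size change is needed.

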12.3.1 Blinding

This is a double-blinded trial in which brodalumab and placebo are visually distinct from each other. The packaging and labelling of the products will contain no evidence of their identity.

Since brodalumab and placebo are visually distinct, the products will be handled and administered by a qualified, unblinded HCP at the site. A blinded study physician at the site will perform clinical assessment of PASI, IGA, BSA, nails, and joints at visit 2, 3, and 4. Subjects are not informed of the visual differences between placebo and brodalumab. Syringes are masked and with no possibility of identifying the content. The only visual difference will be minor color differences. Therefor, subjects will not be aware of the treatment received.

Subjects, investigators (except unblinded HCPs), and nuclear medicine specialists and all staff involved in vascular imaging and analysis is blinded to group assignment.

The trial site will maintain a written plan detailing which staff members are blinded/unblinded.

Trial ID (EudraCT No.): 2017-003697-14	Date: 23.02.2018	Page Version 2.3
---	------------------	---------------------

12.3.2 Emergency unblinding of individual subject treatment

Provisions are in place for 24 hour emergency unblinding of individual subject treatment. If emergency unblinding is required, the investigator can unblind a subject. Emergency envelopes of individual treatment allocation is maintained by the unblinded HCP's at the trial site. For a requester without access to the trial site (e.g., an HCP not involved in the trial), a 24 hour local contact number for the trial site is provided. The requester will provide the subject ID (Danish CPR number) to the staff who will reveal the individual treatment allocation. If necessary, the staff will facilitate contact to the investigators.

12.4 Background treatment (topical agents)

All subjects may use an additive-free, basic bland emollient twice daily and/or topical corticosteroid class II or weaker (danish classification of topical corticosteroids). Subjects are not allowed to start treatment with other prescription emollients including topical corticosteroids class III or stronger during the trial. Other topical and systemic anti-psoriatic treatments are not allowed.

12.5 Concomitant medication and procedures

Concomitant medication and procedures (including diagnosis, intervention, and start and stop date) are recorded in the subject's medical record and the eCRF. Investigators may prescribe concomitant medications or treatments to provide adequate supportive care as deemed necessary, except for medications listed in Section 11.6.

Concomitant medication for conditions other than psoriasis may be continued throughout the trial without any change in dosage whenever possible.

12.6 Prohibited medication and procedures

The following medications are prohibited during the trial from inclusion through week 16:

- Topical corticosteroid treatment (class III or stronger)
- Other topical treatments for psoriasis such as calcipotriol
- Ultraviolet type B phototherapy
- Psoralen plus ultraviolet type A photochemotherapy
- Methotrexate, cyclosporine, acitretin, and fumaric acid esters
- Adalimumab, etanercept, infliximab, cosentyx, ixekizumab, and ustekinumab
- Other immunosuppressive or anti-inflammatory agents including janus kinase inhibitors, interferon-gamma, or other biologics
- Immunoglobulin or blood products
- Systemic corticosteroids (nasal and inhaled corticosteroids are allowed)
- Allergen immunotherapy

Trial ID (EudraCT No.): 2017-003697-14	Date: 23.02.2018	Page Version 2.3
---	------------------	---------------------

- Live (attenuated) vaccine

12.7 Treatment logistics and accountability

12.7.1 Labelling and packaging of investigational medicinal products

The investigational medicinal products will be packaged in individually numbered kits, each containing 1 syringe (broadalumab 210 mg or placebo).

Primary and secondary packaging materials (syringe and outer carton, respectively) will be individually labelled. Labelling will not indicate whether the content of the syringe is broadalumab or placebo.

12.7.2 Storage of investigational medicinal products

Initial storage and relabeling of broadalumab are delegated to the Central Denmark Region Hospital Pharmacy. Products are subsequently delivered to the research facility at the Department of Dermatology, Aarhus University Hospital.

All investigational medicinal products will be stored in a secure and restricted area under the conditions specified on the label and remain in the re-labelled original container until dispensed.

The products will be stored at 2 to 8°C at the site. The temperature during storage will be monitored by a calibrated, stationary and continuously recording system.

A temperature log will be kept to document the storage within the right temperature interval. Storage facilities will be checked at least every working day.

Subject's will be instructed to store Brodalumab for home-use at 2 to 8°C (refer to appendix I for details).

12.7.3 Drug accountability

An inventory (trial medication inventory log) will be kept of the investigational medicinal products administered/provided to each subject randomized in the trial. The trial medication inventory log will be available for inspection during monitoring visits.

Subjects will be provided with sharps bins for used syringes. Filled sharps bins will be returned to the trial site. Subjects will return trial kit cartons, and any unused products at next trial visit.

12.7.4 Trial product destruction

Unused investigational medicinal products as well as used syringes returned to the site will be shipped for destruction by the Department of Dermatology according to local approved procedures.

12.7.5 Treatment compliance

Trial ID (EudraCT No.): 2017-003697-14	Date: 23.02.2018	Page Version 2.3
---	------------------	---------------------

Subjects will record date and injection site for each administration in a log of drug administration; these data will then be transcribed into the eCRF by site staff at the next trial visit. Any non-compliance and the reason for it must be recorded in the eCRF.

If the treatment has been interrupted for any reason (e.g. clinically significant infection) the final visit can be postponed at the investigator's discretion with the number of weeks that the treatment was interrupted.

All used and unused syringes must be returned to the trial site.

12.8 Provision for subject care following trial completion

In order to ensure appropriate treatment of the subjects after they have completed the trial, subjects will be treated at the investigator's discretion or referred to other physicians according to clinical practice and national treatment guidelines. This also applies to subjects that dropout or terminates the study before completing all visits.

12.9 Reporting product complaints

Any defect with the brodalumab device will be reported to LEO Pharma A/S according to standard practice.

13 Trial schedule and assessments

13.1 Overview

Protocol approval (Danish Medicines Agency and Ethical Committee): by November 2017
First patient first visit: December 2017

Patient enrollment and investigational procedures: December 2017 – April 2019

Last patient last visit: April 2019

Data collection completion: May 2019

Data analysis and publication of results: Until January 2020

Evaluations to be done at each visit are shown in the schedule of procedures in Section 7. Refer to Section 10.1 for further details on the trial design.

During the course of the trial, subjects may need to be seen at unscheduled visits. The assessments to be performed at an unscheduled visit are left to the investigator's discretion. Assessment of psoriasis disease severity (PASI, IGA, BSA, nail count, and joint count) after randomization will be performed only by the blinded assessor.

13.2 Assessments performed only at screening/baseline

Assessments performed only at the screening and/or baseline visit include: assessment of

Trial ID (EudraCT No.): 2017-003697-14	Date: 23.02.2018	Page Version 2.3
---	------------------	---------------------

elegibility criteria, demographics, medical history, height, and weight. These are described in further detail below. Laboratory tests include hepatitis B, hepatitis C, HIV-1, HIV-2, T-spot, and serum pregnancy test. Varicella zoster antibody analysis may be relevant in some subjects. Procedures include chest X-ray.

A pre-treatment chart is completed before initiation of treatment according to national guidelines (Appendix III)

13.2.1 Demographics

The following demographic data will be recorded:

- ❑ Month and year of birth
- ❑ Sex
- ❑ Race: Asian, Black or African American, Middle East and North Africa, White, Other

13.2.2 Medical history

Relevant past and concurrent medical history must be recorded and includes:

- Psoriasis medical history: all past and current history including:
 - Duration of psoriasis in years
 - Severity of psoriasis
 - Previous psoriasis treatments
 - Psoriasis clinical manifestations (plaque, scalp, nails, genital/flexural)
 - Family history of psoriasis
 - Co-morbidities including psoriatic arthropathy*, obesity, diabetes mellitus, arterial hypertension, hypercholesterolemia, stroke, ischemic heart disease, and depression
- Other medical and surgical history including concurrent diagnoses.

Relevant medical history includes also diseases which are specifically listed as exclusion criteria and diseases for which specific treatments are listed as exclusion criteria.

*Psoriatic arthropathy: history of formal psoriatic arthritis diagnosis or; pain, stiffness for >30 minutes in the morning / after prolonged inactivity. Improves with activity. Peripheral or with axial involvement – inflammatory back pain and stiffness that improve with activity. Night symptoms.

13.2.3 Height and weight

The subject's height must be measured (without shoes) and weight must be determined (in indoor clothing and without shoes).

Trial ID (EudraCT No.): 2017-003697-14	Date: 23.02.2018	Page Version 2.3
---	------------------	---------------------

13.3 Psoriasis efficacy assessments

13.3.1 Investigator assessments

13.3.1.1 *Investigator's Global Assessment*

The IGA is an instrument used in clinical trials to rate the severity of the subject's global psoriasis and is based on a 5-point scale ranging from 0 (clear) to 4 (severe).⁵² The IGA score will be assessed according to the Schedule of procedures (Section 6). The assessment will be based on the condition of the disease at the time of evaluation and not in relation to the condition at a previous visit (static form of IGA). Assessment at screening is performed by a trained investigator. Assessment at baseline (visit 2) and follow-up (visit 3 and 4) will be performed by a blinded assessor only.

Investigator's Global Assessment

Score	Disease severity
0	Clear
1	Almost clear
2	Mild disease
3	Moderate disease
4	Severe disease

13.3.1.2 *Psoriasis Area and Severity Index*

The most widely used and best validated instrument for assessment of psoriasis disease severity is the *Psoriasis Area Severity Index* (PASI).⁵³⁻⁵⁵ The PASI score rests on a physician's evaluation of the skin area involved, erythema, induration and scaling; and scores range from 0 to 72. Treatment response is assessed as PASI reduction in percentage. Even though there is no definite consensus, moderate-to-severe psoriasis is often defined as a PASI score ≥ 10 .⁵⁶ Assessment at screening is performed by a trained investigator. Assessment at baseline (visit 2) and follow-up (visit 3 and 4) will be performed by a blinded assessor only.

Trial ID (EudraCT No.): 2017-003697-14	Date: 23.02.2018	Page Version 2.3
---	------------------	---------------------

Plaque characteristic	Rating score	Body region (and weighting factor)			
		Head	Upper Limbs	Trunk	Lower Limbs
Erythema	0 = None 1 = Slight 2 = Moderate 3 = Severe 4 = Very severe				
Thickness					
Scaling					
Add together each of the 3 scores for each of the body regions to give 4 separate sub totals.					
Sub Totals		A1=	A2=	A3=	A4=
Multiply each sub total by amount of body surface area represented by that region i.e. A1 x 0.1 for head, A2 x 0.2 for upper limbs, A3 x 0.3 for trunk, A4 x 0.4 for lower limbs to give a value B1, B2, B3 and B4 for each body region respectively					
Degree of involvement as % for each body region affected; (score each region with score between 0-6)		A1 x 0.1 = B1	A2 x 0.2 = B2	A3 x 0.3 = B3	A4 x 0.4 = B4
		B1=	B2=	B3=	B4=
For each body region multiply sub total B1, B2, B3 and B4 by the score (0-6) of the % of body region involved to give 4 subtotals C1, C2, C3 and C4					
		B1 x score = C1	B2 x score = C2	B3 x score = C3	B4 x score = C4
		C1=	C2=	C3=	C4=
The patient's PASI score is the sum of C1+C2+C3+C4				PASI=	

